7.5.2 IV Administration of Tc 99m tilmanocept

IV administration of Tc 99m tilmanocept will be at study time 00:00. The preferred site of IV placement will be the left or right antecubital vein.

Tc 99m tilmanocept shall be administered through the catheter as a slow IV push followed by a 10 cc sterile normal saline flush. The injection will be performed in the nuclear medicine department by an onsite Certified Nuclear Medicine Technologist or Nuclear Medicine Physician.

7.5.3 Post-Injection

The following procedures will be completed at the specified timepoints:

- 0-30 Minutes Post-Injection
 - ECG (completed before vital signs)
 - Vital signs (body temperature, heart rate, systolic and diastolic blood pressure, and respiratory rate) will be collected
 - Assessment of adverse events
- 60-75 Minutes Post-Injection
 - Assessment of adverse events
 - Whole body planar imaging
 - Optional SPECT/CT region(s) of interest imaging

- After the 60-75 Minute Imaging:
 - Clinical labs and urinalysis will be performed.
 - A KS tissue biopsy will be taken of an imaging-visualized non-visceral lesion
 - If no lesion is visualized on imaging, a lesion of at least 5-6 mm in a clinically accessible area will be biopsied as chosen by the Investigator(s) who will record selection and rationale
 - A photograph of the biopsy site with a measurement scale must be taken and stored with the subject's research chart

7.6 Follow-Up Telephone Call (7±3 days after IV Tc 99m tilmanocept injection)

- Concomitant medication review
- Assessment of adverse events

7.7 Imaging and Acquisition of Imaging Data

Imaging will be a whole body planar scan followed by optional SPECT/CT region(s) of interest scan beginning at 60-75 minutes post-IV injection (all Cohorts) and 60-75 minutes and 4-6 hours post-SC injection (Cohort 3 only).

7.8 Image Acquisition

The same scanner should be used during the entire course of the study and any updates to hardware or software should be avoided. If changes occur, they must be reported to the sponsor. Whole body planar with optional SPECT/CT images will be obtained from each subject at the 60-75 minute post-injection timepoint following IV injection (all Cohorts) and at the 60-75 minute and 4-6 hours post-injection timepoints following SC injection (Cohort 3 only).

7.9 Evaluation of Planar and SPECT Images

Tc 99m tilmanocept localization in cutaneous and non-cutaneous lesions will be evaluated through image analysis by the onsite Nuclear Medicine physician. First, an assessment of the overall technical adequacy of the scan will be made. Following the technical assessment, an overall assessment of the scan will be made. For each subject, the de-identified planar images and SPECT/CT scans (in DICOM [digital imaging communications in medicine] format) will be forwarded to the sponsor.

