3 OVERVIEW OF METHODOLOGY AND DESIGN

3.1 Overall Trial Design

This is a prospective, single-center, open-label, non-randomized, dose escalation, comparative, safety study of IV and SC injected Tc 99m tilmanocept in the localization and detection of cutaneous and non-cutaneous KS lesions in subjects with biopsy-confirmed KS. This study includes IV administration of 3 doses Tc 99m tilmanocept: 100 μ g/ 5 mCi, 100 μ g/ 10 mCi and 200 μ g/ 5 mCi. All subjects will receive IV administration at one of these three doses. Cohort 3 will serve as a comparator arm, and Cohort 3 subjects will additionally receive a SC injection of Tc 99m tilmanocept at the Cohort 3 dose of 200 μ g/ 5 mCi. Following IV injection of Tc 99m tilmanocept, all subjects will have whole body planar imaging with optional SPECT/CT imaging beginning 60-75 minutes post-IV injection. Following SC injection of Tc 99m tilmanocept, Cohort 3 subjects will undergo whole body planar imaging with optional SPECT/CT imaging twice: first beginning 60-75 minutes after SC injection, and again 4-6 hours post-SC injection. The Schedule of Events, [Appendix 1](#), contains a list of all study procedures and time-points. Study activities are described in detail in [Section 7](#).

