5.3 Treatment Assignment

In this prospective, single center, open-label, non-randomized, dose-escalation, comparative, safety study, Cohort 1 subjects will receive an IV administration of 100 μ g/ 5 mCi Tc 99m tilmanocept. Cohort 2 subjects will receive an IV administration of 100 μ g/ 10 mCi Tc 99m tilmanocept. Cohort 3 subjects will receive a SC and an IV administration of 200 μ g/ 5 mCi Tc 99m tilmanocept approximately one week apart. Cohort 1 will be the starting dose group. Four subjects will be enrolled into Cohort 1.

If one of the four Cohort 1 subjects experiences a noxious pharmacologic activity/an ADR, two more subjects will be treated at the same tilmanocept mass dose and same radiolabel level as the subject with the ADR. If 2 out of 4 or 3 out of 6 subjects experiences a noxious pharmacologic activity/an ADR in

Cohort 1, the maximum tolerated dose (MTD) cannot be determined. If no additional noxious pharmacologic activities/ADRs are observed in the expanded cohort, the dose escalation will continue with Cohort 2. If one additional noxious pharmacologic activity/ADR is observed, the current dose will be deemed the MTD. If more than one additional pharmacologic activity or ADR is observed in the expanded cohort, the previous dose will be deemed the MTD.

If no noxious pharmacologic activities/ADRs are experienced in Cohort 1, Cohort 2 will be open for enrollment.

Dose escalation will continue until the MTD is found or until Cohort 3 is reached with only one ADR or without any ADRs. The maximum tolerated dose is defined as the highest dose level at which no more than 33% of subjects experienced an ADR. Visual representation of the dose escalation scheme may be found in Appendix 2.

NOTE: Adverse Drug Reaction

An Adverse Drug Reaction (ADR) includes all noxious and unintended responses to a medicinal product related to any dose or dose regimen. The phrase “responses to a medicinal product” means that a casual relationship between a medicinal product and an adverse event is at least a reasonable possibility, i.e. the relationship cannot be ruled out.

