7.1 Screening Visit (within 30 days of Day 1 injection)

- Obtain signed informed consent for study participation
- Preliminary review of inclusion and exclusion criteria
- Allocation of unique subject number; this number will be used to document the subject data in the case report forms (CRFs) and enrollment log
- Interview including the following subject-specific characteristics:
 - Demographic data - date of birth, gender, race
 - Medical/surgical history - all relevant prior medical and surgical conditions will be recorded in the CRF. Documented medical conditions will also note the month and year of onset if the condition is still active.
 - Concomitant Medications (within 30 days before Day 1 injection).
- Vital signs (body temperature, heart rate, blood pressure, and respiratory rate after at least 1 minute in a resting position).
- Electrocardiogram (ECG); subjects will either have a normal ECG or an abnormal ECG deemed not clinically significant by the PI.
- Blood draw for routine hematology, chemistry, serum pregnancy test for women of child-bearing potential. Females of child bearing potential are defined as women that are not surgically sterile (hysterectomy or bilateral oophorectomy) nor postmenopausal for at least 1 year prior to screening. Women who are not of childbearing potential will not require a pregnancy test.
- Urine collection for routine urinalysis.
- Physical examinations will include assessment of height and weight and an examination of general appearance, skin, eyes, ears, nose, throat, head and neck (including thyroid), lungs, heart, abdomen, lymph nodes, musculoskeletal, and nervous system. Any clinically relevant finding is to be documented as a baseline finding. Physical exams that are conducted as standard of care prior to signing informed consent may be used if they are performed within 30 days of injection.
- Assessment of edema/lymphedema, utilizing a pitting edema scale as provided in [Appendix 3](#), will be performed.
- KS history and classification.
- KS Lesion Assessment:
 - Cutaneous KS evaluation: All cutaneous lesions will be identified, documented, and photographed during the screening exam. Photographs will be collected per the photography protocol currently in use within the Department of Dermatology at UCSF, as provided in [Appendix 4](#).

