8.4 Post-Injection and Imaging Biopsy Acquisition

The purpose of the KS lesion biopsy will be to determine the proportion of CD206-expressing cells and quantity of CD206 (IHC fluorescence) in KS tissues in parallel with an analysis of KS imaged with Tc 99m tilmanocept. A non-visceral site of KS for biopsy post-imaging in each subject will be chosen by the Nuclear Medicine physician based on visualized localization and lesion size. If no lesion is determined to localize Tc 99m tilmanocept, a lesion of at least 5-6 mm in a clinically accessible area will be biopsied as chosen by the Investigator(s) who will record selection and rationale.

All subjects will receive the biopsy on the day of IV Tc 99m tilmanocept administration at the completion of imaging.

A biopsy up to 6mm of the designated lesion will be taken, and a photograph of the biopsy site with a measurement scale will be taken and stored with the subject's research chart. The tissue will be obtained at the completion of Tc 99m tilmanocept IV injection and imaging and delivered on ice to the Department of Pathology at Zuckerberg San Francisco General Hospital. The biopsy will be sectioned into a formalin-fixed paraffin-embedded (FFPE) segment and a fresh or frozen segment to be used for other analyses. FFPE tissue sections will be quantified for CD206 and LANA through a standardized quantitative image analysis program. HHV8 will be quantified by qPCR.

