9.3 Efficacy Variables

The efficacy variables for this study are as follows:

- Nuclear medicine specialist determination of presence/absence of illumination (i.e., localization positive/negative, anatomic site) relative to background from SPECT imaging results for each subject;
- Clinically identified presence/absence of KS (based on any previous diagnostic evaluations);
- Quantitative SPECT gamma counts for each biopsied lesion.

The efficacy endpoints for this study are as follows:

- Per subject localization rate of Tc 99m tilmanocept in at least one KS suspected or confirmed lesion by planar and/or SPECT/CT imaging
- Per lesion/region concordance of Tc 99m localization with anatomical areas of active KS defined by confirmed diagnosis or clinical symptomology
- Localization intensity for each biopsied and clinically defined lesion as determined by quantitative SPECT gamma counts
- Per biopsied lesion proportion of CD206-expressing cells and total CD206 as determined by histology and relative IHC fluorescence
- Per lesion/region concordance of IV vs SC Tc 99m localization with anatomical areas of active KS defined by confirmed diagnosis or clinical symptomology.
- Per subject localization rate of Tc 99m tilmanocept in areas other than KS by planar and/or SPECT/CT imaging

- Per area localization rate of Tc 99m tilmanocept in the most frequently identified areas other than KS by planar and/or SPECT/CT imaging

A localized subject is one for whom Tc 99m by planar and/or SPECT/CT imaging results in the illumination of at least one site relative to background as determined by the nuclear medicine specialist.

A localized KS lesion is a lesion that is both clinically identified or suspected KS and planar or SPECT/CT illuminated.

Localization in areas other than KS will also be defined per subject and per area, where these areas are clinically negative KS locations based on clinical symptomology.

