1.2 Study Procedures

The study includes procedures at screening (within 30 days of injection), pre-injection, injection, and post-injection. The post-injection time points include measurements at 30 minutes, 60 - 75 minutes, 4 - 6 hours, and 4 - 10 days post-injection. The following describes the procedures to be conducted on each study day at each time point.

1.2.1 Cohorts 1 and 2

Screening Visit (Visit 1, Day -29 to Day 0): The screening visit will include informed consent, review of study eligibility, allocation of unique subject number, demographic data, medical and surgical history, vital signs (henceforth, vital

signs refers to body temperature, heart rate, systolic and diastolic blood pressure and respiration rate), physical exam including height and body weight, assessment of edema/lymphedema, ECG, blood draw for clinical lab results, cutaneous and non-cutaneous KS evaluation, photographs of all visible cutaneous KS lesions, KS history and classification, urine sample collection for routine urinalysis, urine pregnancy test for women of child-bearing potential, and review of medications.

Pre-tilmanocept Injection (Visit 2, Day 1):

- Concomitant medication review
- A negative urine pregnancy test for women of child-bearing potential
- Vital signs (within 30 minutes preceding injection)

Tilmanocept Injection (Day 1): Based on Cohort assignment, subjects will receive their study drug dose by IV route of administration.

Post-tilmanocept Injection (Day 1):

- Within 30 minutes post-injection
 - ECG (completed before vital signs)
 - Vital signs
 - Adverse event assessment
- 60- 75 minutes post-injection:
 - Adverse event assessment
 - Whole body planar imaging
 - SPECT/CT imaging of region(s) of interest (optional)
 - After the imaging is complete
 - Blood sample for hematology and serum chemistry
 - Urine sample for routine urinalysis
 - Biopsy of designated non-visceral KS lesion
 - Photograph of biopsy lesion with a measurement scale. This image is to be stored within the subject's research file.

Follow-Up Telephone Call (7+3 days post-tilmanocept injection):

- Concomitant medication review
- Adverse event assessment

Each subject's participation in the study is complete after the follow-up telephone call.

For determination of secondary endpoints, the Tc 99m tilmanocept whole body planar and SPECT/CT images will be visually assessed for localization by a Nuclear Medicine Physician.

1.2.2 Cohort 3

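### Nothing masks the onsite reader to the screening lesion record, so imaging-versus-clinical concordance can be biased upward; record and lock each read before that record is opened

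*Protocol*

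**What the plan says.** Protocol 7.9 gives the read to one role: localization "will be evaluated through image analysis by the onsite Nuclear Medicine physician". SAP 1.2 adds only that the "images will be visually assessed for localization by a Nuclear Medicine Physician". Protocol 9.3 defines a localized subject by "illumination of at least one site relative to background as determined by the nuclear medicine specialist", and SAP 1.1.1 repeats the definition. No intensity threshold is set.

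The surrounding design is unmasked. Protocol 3.1 states: "This is a prospective, single-center, open-label, non-randomized, dose escalation, comparative, safety study". The lesion record exists before any scan. At screening (Protocol 7.1), "All cutaneous lesions will be identified, documented, and photographed during the screening exam", and non-cutaneous lesions are also identified and documented.

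The reader's role extends to biopsy. Under Protocol 8.4 the site "will be chosen by the Nuclear Medicine physician based on visualized localization and lesion size", and "All subjects will receive the biopsy on the day of IV Tc 99m tilmanocept administration at the completion of imaging". An IV read is therefore needed that day.

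In Cohort 3, Protocol 5.3 gives SC and IV doses of "Tc 99m tilmanocept approximately one week apart". Protocol 7.4 and 7.5 fix the order: SC on Day 1, IV on Day 7 ± 3.

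Protocol 7.9 has the reader assess technical adequacy and then the scan overall, and sends de-identified images to the sponsor. Neither document says what clinical information the reader holds, when a call becomes final, or whether anyone reads the images a second time.

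**The concern.** Concordance of imaging with clinically defined KS, and of IV with SC localization, are the first and third secondary objectives (Protocol 2.2). Both depend on these visual calls. If the reader knows where the lesions are, faint uptake at a known site is more readily called positive, and similar uptake elsewhere may be discounted as physiological. The index read is then not independent of the clinical reference it is compared with.

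The first tendency raises the localization rates in SAP Tables 5 and 6 and lowers the non-localization rate in Table 8. The second affects Tables 14 and 15 (non-KS sites). Table 7, lesions seen on imaging but not clinically, is the clearest case: its meaning depends on whether the read came before knowledge of the clinical findings. In Cohort 3 the SC result is a further source of prior knowledge for the IV read.

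**Working it through.** **The plan's own figure.** The only relevant number in the documents is the sample size: 4 + 4 + up to 6 = up to 14 (Protocol 9.4), which reproduces. No expected concordance, reader agreement or power is stated, so every rate below is an assumption and shows direction and order of size only.

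**Imaging versus clinical, simple example.** Assume 60% of lesions are clearly positive, 20% equivocal and 20% clearly negative. Assume equivocal lesions are called positive 80% of the time when the sites are known and 50% when they are not.
- Sites known: 0.60 + 0.20 × 0.80 = 0.76
- Sites not known: 0.60 + 0.20 × 0.50 = 0.70

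**Imaging versus clinical, range.** Let s be the rate an unaided reader would call, and b the share of the remaining lesions called positive because their place is known. Observed rate = s + (1 − s)b.

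| s | b = 0 | b = 0.1 | b = 0.2 | b = 0.3 |
|---|---|---|---|---|
| 0.50 | 0.50 | 0.55 | 0.60 | 0.65 |
| 0.70 | 0.70 | 0.73 | 0.76 | 0.79 |
| 0.90 | 0.90 | 0.91 | 0.92 | 0.93 |

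The simple example is the cell s = 0.70, b = 0.2. In this model knowledge of the sites can only add positives at known lesions. Locking the read before the record is opened sets b to 0.

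**IV versus SC, anchoring on the SC result.** Let a be the unbiased agreement and c the share of discordant IV calls moved to the SC call. Agreement = a + (1 − a)c. With a = 0.70 (IV-only 0.25, SC-only 0.05):
- c = 0.2: 0.76
- c = 0.3: 0.79
- c = 0.5: 0.85

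Power of the exact McNemar test, at an assumed two-sided 0.05 with 30 sites treated as independent, falls from 0.40 to 0.28, 0.22 and 0.09 respectively.

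**IV versus SC, other mechanisms.** Start from 0.40 both localized, 0.15 IV-only, 0.15 SC-only and 0.30 neither, so agreement is 0.70.
- Lean toward positive IV calls: a share e of IV-negative sites is called IV-positive. Agreement = 0.40 + 0.15e + 0.30(1 − e) = 0.70 − 0.15e, giving 0.685 at e = 0.1 and 0.655 at e = 0.3. Rejection by McNemar at 30 sites rises from 0.02 to 0.03 and 0.15.
- Lesion knowledge acting independently on both reads: agreement = 0.40 + 0.30b + 0.30b² + 0.30(1 − b)² = 0.70 − 0.30b + 0.60b², giving 0.676 at b = 0.1 and 0.664 at b = 0.2 and 0.3.

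So anchoring raises agreement and hides a difference, while a lean toward IV lowers agreement and can create one. The direction for Table 9 is not fixed.

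**Size of the task.** One planar read per subject in Cohorts 1 and 2 and three per subject in Cohort 3 gives at most 4 + 4 + 6 × 3 = 26 planar reads to lock, plus any optional SPECT/CT.

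**The case against.** The strongest reply is that this is a small Phase 1 safety study. Its primary variable is the ADR (Protocol 9.2), SAP 2.1 calls all results descriptive, and no concordance threshold decides anything. That limits the stakes and stands. It does not remove the gap, because concordance is what the study will report about imaging performance.

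A reader might also infer several stronger things that the documents do not support.
- *That the reader will have the lesion record.* No section says so. Biopsy selection by lesion size makes it plausible, but Protocol 8.4 names visualized localization and size, not the screening form. The documents leave it open.
- *That both concordance endpoints are inflated.* Only imaging versus clinical has a likely direction; IV versus SC can move either way.
- *That a lock by the same physician cures both.* In Cohort 3, if one physician reads both routes, that physician read the SC scan 4 to 10 days before the IV scan, in at most six subjects. A lock does not erase that memory.
- *That the bias could never be undone.* Re-analysis of the recorded calls cannot separate tracer uptake from prior knowledge. The images are kept and sent to the sponsor (Protocol 7.9, 8.3), however, so a masked re-read is possible, although none is planned.

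Two practical objections have force. The site codes in Protocol Appendix 5 are cutaneous only, and a focus locked as one limb cannot be assigned to one of many lesions there without a further judgement. Also, if clinical lesion sites guide the choice of optional SPECT/CT regions, those images are not independent of the lesion record, and a read lock does not change that.

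**Conclusion.** The gap is real: a subjective, threshold-free call by one onsite physician, with no masking, read order or lock in either document. It can bias imaging-versus-clinical concordance upward in Tables 5 and 6, with the mirror effect in Table 8, and it clouds Tables 7, 14 and 15. The size is unknown. The 0.76 versus 0.70 example, and the wider 0.73 to 0.79 around an unaided 0.70, rest wholly on assumed rates and on the reader actually knowing the lesion sites.

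For IV versus SC the comparison is unmasked and its bias has no fixed direction. The power figures assume 30 independent sites; clustering within at most six subjects makes them approximate. The primary ADR endpoint and the sample size are not affected. The change is worth making because it is cheap and fits a sequence the protocol already requires.

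**What to change.** Add to Protocol 7.9 and the SAP a two-step read by the same physician.

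1. On each scan, before opening the lesion record, record all foci by anatomical location, then lock and time-stamp the entry. The location list must extend beyond the Appendix 5 skin codes to oral, visceral and non-KS sites.
2. Then open the lesion record, match foci to lesions under a rule stated in advance (including how to treat several lesions in one location), and select the biopsy lesion as the protocol already provides.

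Use only the locked calls for SAP Tables 5 to 9, 14 and 15.

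For Table 9, either report the IV-versus-SC comparison as unmasked, or base it on a later coded, mixed-order re-read of the stored images by the same reader. In either case note that tracer at the ankle or foot injection sites may still reveal the route.

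The cost is a read form, a few minutes before biopsy selection, and possibly a slightly lower concordance figure. No subject, scan or reader is added, and the biopsy rules are unchanged. The optional re-read costs reader time only.

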7.10 End of Study

For the entire study, end of study is defined as the follow-up telephone call.

8 PROCEDURES AND VARIABLES

8.1 Population Characteristics

8.1.1 Demographic and Other Baseline Characteristics

Up to fourteen (14) HIV-positive female or male subjects \geq 18 years that have been diagnosed with biopsy-confirmed KS will be enrolled, injected, and imaged. There are no minimum or maximum numbers for gender in the cohorts.

8.1.2 Medical and Surgical History

Relevant medical and surgical histories, specifically for HIV and KS, will be obtained on all study subjects.

As part of the medical history, the date of the last spontaneous menstruation will be recorded, if childbearing potential is not excluded by surgical sterilization.

